### Primary Endpoint Analysis and Statistical Considerations (Efficacy):

The hypothesis is that sirolimus will prevent or delay seizure onset in infants with TSC up to 12 months in age. To evaluate efficacy, we will determine time to seizure onset after treatment initiation in infants treated with sirolimus.

It was originally planned for this analysis to consist entirely of subjects enrolled into Stage 2 (n=60), comparing time to seizure onset between the two groups (treatment vs. placebo). With Stage 2 now eliminated from this protocol, we will instead use a contemporary, prospectively evaluated historical control group (n=32) from our TACERN/TSC-EBS natural history study for comparison (Wu et al. Epilepsia 2019. 60:2428-36), in which infants were similarly enrolled 0-6 months of age and followed until 24 months of age. Instead of time to seizure onset for the comparative analysis, we will use age of seizure onset as the outcome of interest as there was no treatment in the TACERN/TSC-EBS studies to use as a start point. The average age of seizure onset in the TACERN/TSC-EBS control group was 7.4 ±4.4 months. For statistical significance, we will use t-test or Wilcoxon rank sum test for the differences, depending on distribution (parametric vs. nonparametric). In addition, survival analysis will be conducted with statistical comparison between treatment groups utilizing the long-rank test. Seizure frequency, and history of infantile spasms at 12 months of age have been shown to be predictive of long-term neurodevelopmental outcome and seizure control at 24-36 months of age. Therefore, we will similarly compare seizure frequency at 12 months of age using the t-test/Wilcoxon rank sum test and the proportion of subjects who develop infantile spasms (past or current) using Fisher's exact test.

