**Sirolimus for treatment of refractory epilepsy in TSC:** Sirolimus is FDA approved for the treatment of LAM, a progressive lung disease largely seen in adult women with TSC. Sirolimus has also been shown to be effective for treatment of TSC-associated SEGA, angiomyolipoma, cutaneous hamartomas, retinal hamartomas, and cardiac rhabdomomas. Yet despite robust preclinical studies demonstrating reduced seizures in TSC animal models treated with sirolimus, clinical development of mTOR inhibitors for the treatment of epilepsy in patients has almost exclusively focused on everolimus. Case reports and retrospective studies have reported reduced seizure frequency following the initiation of treatment with sirolimus, but to date there has been only one prospective clinical trial. Twenty-three children with TSC ages 1.8-10.9 years were treated with open-label sirolimus for 6 months. Half were randomized to treatment immediately, the remainder to treatment 6 months later. Sirolimus treatment reduced seizure frequency 41% compared to standard care, greatest in those achieving a target trough level of 5-10 ng/mL, and 3 patients became seizure-free. The trial was limited, however, by failing to reach its inclusion goal of 30 children.

**Safety of mTOR inhibitors in TSC Infants:** Multiple prospective clinical trials have demonstrated safety and tolerability of mTOR inhibitors generally in TSC, including sirolimus. Because treatment in each of the trials was initiated after the onset of clinically significant symptoms, nearly all study participants were over the age of 2 years; safety in younger infants that would be ideally targeted prior to emergence of first seizures remains inadequately studied. There are increasing number of published case reports of successful treatment of TSC infants treated for other indications,  but no prospective studies to date. As part of an international collaboration of TSC specialty clinics, we collected retrospective safety data from TSC infants treated with everolimus (n=39) or sirolimus (n=11) for clinical indications since 2010, when everolimus was first approved for treatment of SEGA. In this cohort, infants

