## **4 STUDY OBJECTIVES AND OUTCOME MEASURES**

## 4.1 Primary Endpoints

1. Safety: The primary endpoint will be the percentage of subjects reporting severe (CTCAE v5.0 grade  $\geq$ 3) adverse event (AE) or serious adverse event (SAE), when treated with sirolimus (TAVT-18). Additional safety-related endpoints include:

- a. Percentage of subjects that reduce or discontinue treatment due to an AE or SAE (any grade).
- b. Number of days treatment is withheld due to an AE or SAE (any grade).

2. *Efficacy*: The primary endpoint for efficacy will be time to seizure onset, when treated with sirolimus (TAVT-18). Additional efficacy-related endpoints include:

- a. Age at time of seizure onset
- b. Percentage of subjects with infantile spasms (past or current) at the end of the treatment period (12 months of age).
- c. Seizure frequency at the end of the treatment period (12 months of age).

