## **5 STUDY DESIGN AND ORGANIZATION**

This trial originally planned to use a two stage, phase I clinical trial design, with the first stage to employ an open-label clinical trial design to verify dosing for TAVT-18 (sirolimus) powder for oral solution in TSC infants (N=5) that would then be carried forward to inform appropriate initial dosing, dosing frequency, and dosing adjustments for the second stage—a randomized, double-blind, placebo-controlled multi-site trial design—to evaluate the safety and efficacy of early sirolimus treatment to prevent epilepsy in TSC infants until 12 months of age (N=60). However, with the elimination of the planned second stage which has now been replaced by STOP2B: TSC-STEPS, the study design now consists of a single stage, phase I clinical trial design only. Subjects will be between 0-6 months of age at time of treatment initiation and meet clinical and/or genetic diagnostic criteria for TSC and have no prior history of clinical seizures at time of enrollment. Treatment will be continued until subjects reach 12 months of age. The TSC Clinic at Cincinnati Children's Hospital Medical Center (CCHMC) will serve as the single clinical site.

Additional key investigators of the study:

- [name] (CCHMC) will direct EEG acquisition and data transfer quality control, processing, and blinded central analysis
- [name] (UNC, Chapel Hill) will direct neuropsychological assessments and data transfer quality control, processing, and blinded central analysis
- [name] [name] (CCHMC) will direct PK/PD sample acquisition and quality control, processing, and blinded central analysis
- [name] (Boston Children's Hospital) will direct dMRI acquisition and data transfer quality control, processing, and blinded central analysis
- [name] (CCHMC) will serve as study biostatistician

Operations will be managed through the Clinical Coordinating Center (CCC) and Data Management Center (DMC) at CCHMC to ensure the optimal scientific rigor, efficient execution and management of the study, and analyses.

An independent medical monitor (MM) and Data Safety Monitoring Board (DSMB) will be established to ensure patient safety is appropriately monitored and prioritized throughout the study.

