## 9.2 CONCURRENT MANAGEMENT OF EPILEPSY

The purpose of the study is to determine if sirolimus is safe and effective for prevention of epilepsy in at-risk infants diagnosed with TSC. The primary endpoint for efficacy epilepsy prevention is time to first seizure (seizure onset). However, subjects treated with sirolimus may still develop seizures if (1) our primary hypothesis is incorrect and sirolimus is not preventative or (2) our hypothesis is correct and seizure onset is delayed but sirolimus does not fully eliminate seizures from ever occurring. It is this very reason that our study will evaluate additional secondary efficacy disease-modifying outcome measures relating to epilepsy (seizure type and seizure frequency) and neurodevelopment at 12 months of age.

Accordingly, new onset of seizures (clinical or electrographic) does not require discontinuation of study medication. New onset of seizures should be evaluated and treated with conventional anticonvulsant medications (note that mTOR inhibitors are excluded) according to recommended clinical practice guidelines and the managing clinician's best judgement. In most instances, this will be initiation of vigabatrin, recommended first line therapy for infantile spasms in TSC and an effective treatment for focal epilepsy which is also common at this age. Rescue medications are also allowed. In all instances, prescribed treatment for seizures (medication, diet, and/or procedures) will be recorded in the appropriate CRF, including medication/treatment/procedure name, start/end dates used, total daily dose prescribed (including dosage adjustments, when applicable). Medications temporarily utilized or prescribed for use on as needed basis (PRN) will be recorded and include the date/time/dose for each use.

Another clinical scenario with relevance to the current study is the potential for off-label, prophylactic treatment with vigabatrin in TSC infants who have not yet experienced clinical or electrographic seizures. Off-label prophylactic treatment with vigabatrin has the potential to directly interfere with primary and indirectly affect secondary outcome measures of this study evaluating the preventative benefit of sirolimus. Jóźwiak et al (2011) published a case series of 14 TSC infants prophylactically treated with vigabatrin following abnormal EEG, compared to

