## Follow-up Visits

In-person study visits will occur at screening/baseline, Day 7, +1 month following treatment initiation, and then at defined intervals thereafter according to subject's chronological age: 3 months, 6 months, 9 months, and 12 months. Visit schedule windows are +/- 2 weeks from the scheduled visit date, and if the +1 month follow-up visit and the next defined age interval follow-up visits are within 4 weeks of each other, they may be combined into a single in-person study visit. At each visit, a clinical examination with interval medical history that includes concomitant medications and any additional interventional therapies received (including type of intervention and average hours/week of each), safety laboratory studies including sirolimus level, optional biorepository samples, EEG, and study drug accountability will be completed. Seizure diaries and adverse event monitoring and reporting will also be maintained continuously throughout the study and reviewed at each visit. At the in-person follow-up visit at 12 months of age, dMRI, EEG, TAND Checklist, VABS, and Bayley-4 will be performed. To verify durability of treatment effect, at the in-person follow-up visit at 24-months of age, repeat developmental assessment with the addition of the PLS-5 and ADOS-2, accompanied by clinical

examination and an interval medical history that will include any additional treatment interventions, epilepsy history, and therapies, will also be performed.

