#### End of Treatment

At the end of the treatment period (when each subject reaches 12 months of age), participants will stop taking the study drug (TAVT-18). Due to the extended half-life of sirolimus, gradual weaning is not necessary. In the absence of significant complications or contraindications, parents who wish to pursue continued treatment with sirolimus after their final study visit as an off-label clinical treatment using commercially-available, FDA-approved medication may do so through consultation with the primary TSC clinician. However, such is not part of the current research study and no research study medication will be provided after completion of the final study visit at 12 months of age.

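### The seizure hypothesis and both fixed-time seizure measures stop at 12 months on treatment, seizure onset has no stated censoring age, and the 24-month epilepsy history has no specified analysis

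*Combined protocol and SAP*

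**What the plan says.** The efficacy hypothesis in section 16.1 is: "The hypothesis is that sirolimus will prevent or delay seizure onset in infants with TSC up to 12 months in age". Section 5 fixes exposure to the same age: "Treatment will be continued until subjects reach 12 months of age". The End of Treatment paragraph confirms that at that point "participants will stop taking the study drug (TAVT-18".

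Section 4.1 defines the endpoints. The primary one reads "The primary endpoint for efficacy will be time to seizure onset, when treated with sirolimus (TAVT-18"; no cut-off or censoring age is attached to it, or to age at onset. Two further measures are tied to the end of treatment: infantile spasms (past or current), and "Seizure frequency at the end of the treatment period (12 months of age".

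Section 16.1 compares age at onset with 32 historical controls followed to 24 months, whose onset age is given as 7.4 ± 4.4 months. It plans a t-test or Wilcoxon test plus a log-rank comparison.

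Section 9.2 describes the seizure and developmental readings as "additional secondary efficacy disease-modifying outcome measures relating to epilepsy (seizure type and seizure frequency) and neurodevelopment at 12 months of age".

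Treated infants return at 24 months. The Follow-up Visits text provides for an "interval medical history that will include any additional treatment interventions, epilepsy history, and therapies", and Post-treatment follow-up adds seizure types and frequency, with an interest in correlating 12-month and later outcomes. Table 3 schedules seizure-diary review up to 12 months and not at 24. Section 16 names no analysis of seizures after 12 months.

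**The concern.** Section 3 reports of an open-label trial in children: "Sirolimus treatment reduced seizure frequency 41% compared to standard care". It also reports a median 73% reduction with everolimus. These are effects on seizures already occurring, seen while the drug was taken. A purely symptomatic drug could therefore also give a later first seizure, fewer spasms or a lower seizure frequency by 12 months. A reading taken on the last day of treatment cannot tell that from a changed disease course.

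Two things are at stake. One is what the trial may say: section 2 presents it as an evaluation of disease-modifying, preventive therapy. The other is what is carried forward: section 16.2 says the descriptive results will inform effect size and sample size for later trials. An on-treatment effect carried forward as prevention would mislead that planning.

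The missing censoring age adds a separate problem. If treated onsets are cut at 12 months and control onsets are not, the age-at-onset comparison uses different observation windows.

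**Working it through.** The plan gives no power, event count or 24-month seizure rate for the current design, so there is no figure of its own to reproduce. Two checks were made.

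**1. Does the observation window matter for the control figure?**

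Inputs: mean 7.4 and SD 4.4 months, controls followed to 24 months (section 16.1). Assumption: onset ages have a normal, gamma or lognormal shape.

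- Share of control onsets after 12 months. Normal: 1 − Φ((12 − 7.4)/4.4) = 1 − 0.852 = 0.148, or 0.155 if truncated to 0–24 months. Gamma: 0.141. Lognormal: 0.124. So about 12–16%.
- Mean of control onsets occurring by 12 months: 6.1 (gamma) or 6.7 (normal truncated at 0 and 12), against 7.4 as quoted.

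The quoted control mean may therefore include onsets that treated infants could not contribute if cut at 12 months. A log-rank test is not distorted by this, because after 12 months no treated infant would be at risk. A t-test or Wilcoxon test on ages is affected.

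**2. Can the 12-month readings separate suppression from a lasting effect?**

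Documented inputs: 70% of infants have seizures in the first year (section 2; a background figure, not stated for the 32 controls) and five treated infants (section 16.2). Assumptions: entry at 3 months, constant hazard to 12 months, and an on-drug hazard ratio (HR) for first seizure.

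No HR is given in the documents. Two values are tried. The first is 0.3. The second is 1 − 0.41 = 0.59, which borrows sirolimus's frequency reduction as if it were a hazard ratio.

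- Hazard: λ = −ln(0.30)/12 = 0.1003 per month.
- Controls free at 12 months, given free at 3: exp(−0.1003 × 9) = 0.41.
- Treated at 12 months: exp(−0.3 × 0.1003 × 9) = 0.76, or exp(−0.59 × 0.1003 × 9) = 0.59. Each is the same under either mechanism.
- Control incidence by 24 months (I): 0.70/0.852 = 0.82 if onset ages are normal; varied from 0.75 to 0.90.
- Control survival from 12 to 24 months: q = (1 − I)/0.30, which is 0.595 at 0.82.
- Treated, seizure-free at 24 months: S(12) × q if the effect ends with the drug; S(12) × q^HR if it lasts.

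| HR | I by 24 months | Free at 12 months | Free at 24, effect ends | Free at 24, effect lasts | Gap, children of 5 |
|---|---|---|---|---|---|
| 0.3 | 75% | 76% | 64% | 72% | 0.4 |
| 0.3 | 82% | 76% | 45% | 65% | 1.0 |
| 0.3 | 90% | 76% | 25% | 55% | 1.5 |
| 0.59 | 75% | 59% | 49% | 53% | 0.2 |
| 0.59 | 82% | 59% | 35% | 43% | 0.4 |
| 0.59 | 90% | 59% | 20% | 31% | 0.6 |

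If every withheld seizure appeared after withdrawal, treated infants would match controls: 0.41 × q = 24% at I = 82%.

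The 12-month column does not depend on mechanism and the 24-month columns do. The gap is at most about one and a half children in five.

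**The case against.** The strongest reply is that the plan claims less than this point implies. The hypothesis says prevent or delay and is itself bounded at 12 months. Section 9.2 openly allows that onset may be delayed without seizures being eliminated. Section 16.2 calls the study a pilot without power for definitive analysis. Section 16.1 justifies the 12-month measures as predictors of outcome at 24–36 months. On-drug delay would support the hypothesis as worded, and that stands. It does not reach the disease-modifying label. Nor do the documents show that the predictive link holds when the 12-month value is read on a seizure-suppressing drug.

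Three stronger readings are tempting and not supported:

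- *Every efficacy measure ends at 12 months.* Only seizure frequency and spasms are fixed there. Onset has no stated cut-off, and developmental testing, EEG and dMRI are scheduled at 24 months, the developmental testing expressly for durability.
- *An infant who first seizes a month after withdrawal counts as seizure-free.* That presumes censoring at 12 months, which the plan does not state. The Follow-up Visits text also says seizure diaries run throughout the study, although Table 3 schedules no review at 24 months.
- *The 24-month seizure data go unused.* Post-treatment follow-up states an intended correlation, and the control onset figure may already include later onsets. What is missing is a specified method.

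It is also fair that a 24-month analysis would not settle the mechanism. Families may continue commercial sirolimus, anticonvulsants may be in use, and there are five infants.

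**Conclusion.** The point holds in a limited form. The 12-month seizure frequency and spasms readings, and onset counted to that age, describe seizures during treatment. They cannot support lasting prevention or disease modification. The plan leaves the censoring age for onset unstated in a comparison where the two cohorts may have been observed for different lengths of time, and it gives no method for the 24-month epilepsy history.

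The size is modest. Under the assumed hazard ratios of 0.3 and 0.59 and 24-month control incidence of 75–90%, the two mechanisms look identical at 12 months and differ by 0.2 to 1.5 children of five at 24 months. These are illustrations resting on undocumented hazard ratios and an inferred 24-month incidence. They also assume that all five infants are off mTOR inhibitors after 12 months. A reader should not infer that the trial is bound to misreport suppression as prevention, or that a 24-month analysis of five infants could test prevention. The case for change rests on its low cost and on the use planned for these estimates.

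**What to change.** In section 16.1:

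1. State one censoring age for seizure onset, applied to both cohorts, for the 12-month comparison. Recalculate the control onset summary on that window.
2. Add a descriptive first-seizure curve to 24 months in both cohorts, split at 12 months, and describe 24-month seizure frequency in treated infants. Mark each treated infant's mTOR-inhibitor and anticonvulsant use after 12 months. Anticonvulsants matter because they affect seizure frequency and, if started before a first seizure, onset as well. Record the date of first seizure on the 24-month CRF.
3. State that the 12-month result concerns seizure onset and frequency during treatment, and that the 24-month display is descriptive and does not test prevention. Bring the wording of section 9.2 into line.

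The cost is SAP wording, one CRF date and a check that control onset ages are available to 24 months. The visit, the treatment history and the control follow-up already exist. The downside is that with five infants, some perhaps still on commercial sirolimus, the off-drug interval is only suggestive.

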## 8.1 Inclusion Criteria

- 0-6 months of age at the time of enrollment (subject must be <7 months of chronological age at time of randomization and treatment initiation). Corrected age must be at least 39 weeks (calculated by subtracting the number of weeks born before 40 weeks gestation from the chronological age).
- 2. Has a confirmed diagnosis of TSC based on established clinical or genetic criteria

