## 8.2 Exclusion Criteria

- 1. Prior history of seizures (clinical or electrographic) at the time of enrollment or identified on baseline EEG
- 2. Has been treated in the past or is currently being treated at the time of enrollment with conventional anticonvulsant medications (AEDs), systemic (oral) mTOR inhibitors (such as rapamycin, sirolimus, or everolimus), ketogenic-related special diet, or another anti-seizure therapeutic agent, device, or procedure
- 3. Has taken any other investigational drug as part of another research study, within 30 days prior to the baseline screening visit
- 4. Has a significant illness or active infection at the time of the baseline screening visit
- 5. Has a history of significant prematurity, defined as gestational age <30 weeks at the time of delivery, or other significant medical complications at birth or during the neonatal period that other than TSC would convey additional risk of seizures or

neurodevelopmental delay (i.e. HIE, severe neonatal infection, major surgery, prolonged ventilatory or other life-saving supportive care or procedures)

- 6. Abnormal laboratory values at baseline (i.e., renal function, liver function, or bone marrow production) that are in the opinion of the investigator clinically significant and may jeopardize the safety of the study subject
- 7. Prior, planned or anticipated neurosurgery within 3 months of the baseline visit
- 8. Has a TSC-associated condition for which mTOR treatment is clinically indicated (i.e. SEGA or AML)
- 9. Subjects who are, in the opinion of the investigator, unable to comply with the requirements of the study

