## 16.2 Study Size and Power Calculations

The original study was powered for the planned enrollment of Stage 2, in which 60 subjects were to be randomized 2:1 for treatment with TAVT-18 (sirolimus) vs. placebo. These power calculations remain valid for STOP2B: TSC-STEPS (CCHMC IRB#2021-0438) that has replaced Stage 2 of the current study. However, with enrollment under the current protocol now limited to Stage 1 only (n=5), this study is no longer powered for definitive analysis and becomes a true pilot study aimed at obtaining preliminary data with regard to potential treatment safety concerns and an estimation of patient variability in treatment response. Analyses for statistical significance will still be carried out with the modifications as outlined above, but it is expected that unless the treatment effect size is very large compared to a similarly matched historical cohort from the TACERN/TSC-EBS study, statistical significance will not be achieved with such a low number of treated individuals in this study. Nonetheless, descriptive analysis as a pilot study using sirolimus (TAVT-18) in a patient population (TSC infants 0-12 months of age) that has hereto never previously been studied in a prospective fashion still has immense scientific and clinical value. Furthermore, should the TAVT-18 sirolimus formulation be further developed as a potential clinical treatment for this indication, the descriptive statistics will provide essential data for estimating potential treatment effect size and interpatient variability values that will prove essential for determining study size and study power.

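### Age at seizure onset is counted from birth although treated infants must be seizure-free when they enter; without delayed entry, the comparison with historical controls can be distorted in either direction

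*Combined protocol and SAP*

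**What the plan says.** Section 16.1 (efficacy) keeps a within-group description: "we will determine time to seizure onset after treatment initiation in infants treated with sirolimus". For the comparison with the TACERN/TSC-EBS natural-history infants it changes the outcome: "Instead of time to seizure onset for the comparative analysis, we will use age of seizure onset as the outcome of interest". The reason given is "as there was no treatment in the TACERN/TSC-EBS studies to use as a start point". Onset age is to be tested by t-test or Wilcoxon, with a log-rank test in addition. Delayed entry, a landmark age and alignment of entry ages are not mentioned.

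Entry for treated infants is conditional on two things. Section 8.1 sets the age: "subject must be <7 months of chronological age at time of randomization and treatment initiation". Section 8.2, criterion 1, excludes: "Prior history of seizures (clinical or electrographic) at the time of enrollment or identified on baseline EEG".

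Of the controls, section 16.1 says only "in which infants were similarly enrolled 0-6 months of age and followed until 24 months of age", with a mean onset age of 7.4 ± 4.4 months (n=32). Section 16.2 calls them "a similarly matched historical cohort from the TACERN/TSC-EBS study" but names no matching variable or procedure.

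**The concern.** An infant who starts sirolimus at 5 months has, by the entry rule, no seizure in the first 5 months. Counted from birth, those months still enter the outcome. In the log-rank test the infant sits in the risk set for every control event before 5 months without being able to have one. In the t-test the infant's onset age has a floor of 5 months.

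Whether this shifts the comparison depends on how the controls entered, and the plan does not say. If they had to be seizure-free at similar ages, the same floor applies to both groups and cancels. If not, a difference appears that has nothing to do with the drug.

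The stated reason for the change does not require an origin at birth. Controls have no treatment start, but they do have an enrolment age.

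Section 16.2 says significance tests will still be run, and that the descriptive results should help estimate effect size and variability if this formulation is developed further. A distorted estimate would harm that use whatever the p-value.

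**Working it through.** The plan states no sample size, power or alpha for this comparison, so there is no planned figure to reproduce. The control mean of 7.4 ± 4.4 months cannot be rebuilt without the control data. The check asks what the planned analysis gives when the drug does nothing.

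**Inputs from the documents.** 5 treated, 32 controls; onset mean 7.4, SD 4.4 months (16.1, 16.2); entry below 7 months (8.1); seizure-free at entry (8.2); 70% seizing in the first year (section 2); treatment to 12 months (section 5).

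**Assumptions.** Onset ages are gamma; entry ages are uniform over the ranges shown; tests are two-sided at 0.05.

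**Step 1, onset model.** Shape = (7.4/4.4)² = 2.83. Scale = 4.4²/7.4 = 2.62 months. The gamma gives P(onset < 12) = 0.859, so the share who ever seize is 0.70/0.859 = 0.815.

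**Step 2, log-rank test censored at 12 months.** Expected treated events are E = Σ dⱼ·n₁ⱼ/nⱼ over event ages tⱼ, where dⱼ is the number of events, n₁ⱼ the treated at risk and nⱼ all at risk. From birth, an infant counts in n₁ⱼ at every tⱼ up to exit. With delayed entry, the infant counts only if entry age < tⱼ. Observed/expected in the treated, with no drug effect (ranges are over repeated runs of at least 1,000 simulated trials):

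| Treated enter (months) | Controls | O/E from birth |
|---|---|---|
| 0-6.9 | not selected as seizure-free | 0.80-0.81 |
| 4-6.9 | not selected as seizure-free | 0.64-0.65 |
| 4-6.9 | seizure-free, enter 0-3 | 0.66-0.67 |
| 4-6.9 | seizure-free, enter 0-6.9 | 0.77-0.79 |
| 0-6.9 | seizure-free, enter 0-6.9 | 0.99-1.01 |
| 0-3 | seizure-free, enter 0-6.9 | 1.19-1.21 |
| 0-3 | seizure-free, enter 3-6.9 | 1.44-1.47 |
| 0-3 | seizure-free, enter 4-6.9 | 1.58 |

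With delayed entry every row is 0.98-1.02.

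**Step 3, mean onset age.** If onsets are not cut off, E[T | T > a] is 8.2, 8.8, 10.3 and 11.0 months for entry at a = 3, 4, 6 and 6.9. Against 7.4 that is +0.8, +1.4, +2.9 and +3.6. Lognormal and Weibull forms with the same mean and SD give similar shifts (+0.5 and +1.0 at 3 months; about +3.7 just under 7 months).

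If treated onsets are counted only to 12 months, E[T | a < T < 12] is 6.8, 7.3, 8.5 and 9.1. Against 7.4 that is -0.6, -0.1, +1.1 and +1.7. The window therefore changes even the sign. Section 16.1 does not fix it: treatment ends at 12 months, controls were followed to 24, and section 11.5 also collects epilepsy history at 24 months.

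**Step 4, false benefit with 5 treated (nominal 2.5% in the favourable direction).** The log-rank test from birth gives 1.6-5.7% in the rows where treated infants enter older, controls are unselected, or the groups match. The t-test with unselected controls and onsets not cut off gives 9-15%. The delayed-entry log-rank test gives 0.5-3.5%. For scale, 5 against 32 with SD 4.4 has 80% power only for a difference of about 5.9 months, and about 16% power at 2 months.

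**The case against.** The strongest reply is that the controls' months before enrolment also count from birth, and the plan says they were enrolled over the same age range. If they were seizure-free at entry with similar ages, nothing is distorted, as the fifth row of the table shows. The group's earlier EEG work, cited in the protocol, concerned asymptomatic infants, which makes seizure-free controls plausible. This stands as far as it goes. It defeats the tempting inference that seizure-free time before treatment is simply credited to sirolimus: the documents settle neither the direction nor the presence of a net bias. Treatment follows TSC diagnosis and may begin from 0 months, so treated infants could well enter younger, and the error would then run against the drug. Nor do the documents show that controls with earlier seizures were included; they are silent.

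A reader might also infer that this is the only comparative efficacy result. It is not: section 16.1 also compares seizure frequency and infantile spasms at 12 months.

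Finally, section 16.2 calls the study an unpowered pilot, expects no significance unless the effect is very large, and makes use for later planning conditional on further development. The replacement randomized trial keeps its own power calculation. This limits the consequence. It does not remove the defect: a shared age range fixes neither seizure status nor the spread of entry ages, and five infants can by chance enter older or younger than 32 controls.

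**Conclusion.** The point holds in this form: treated onset ages are left-truncated at entry, the planned tests ignore it, and the information needed to judge the net effect is not stated. Under the assumed onset model and no drug effect, the treated event ratio can fall to about 0.64 or rise to about 1.5 (1.58 in the most extreme entry pattern tried), and it is 1.0 only when entry ages and the seizure-free rule agree. A spurious shift in mean onset age is possible, but no single figure for it is warranted while the follow-up window is open. If 7.4 ± 4.4 already describes infants who were seizure-free at entry, the net distortion is smaller than the unselected-control rows suggest. Severity is moderate. This is a cheap improvement to an estimate that may be reused, not a flaw that invalidates a five-infant pilot.

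**What to change.** In section 16.1:

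- Keep age as the time scale, but start each infant's risk at entry age: treatment start for treated infants, enrolment for controls. Use Kaplan-Meier and log-rank with delayed entry, and report numbers at risk.
- Restrict controls to infants who meet exclusion criterion 1 at their own entry age, and report entry ages for both groups.
- Censor both groups at the same age, 12 months (end of treatment).
- Drop the t-test/Wilcoxon on onset age, or compare each treated infant only with controls still seizure-free at that infant's starting age, over the same window.
- Delete the claim of matching in section 16.2 unless this is done.

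The cost is plan wording and minor programming. Control enrolment ages and entry EEGs must be obtainable from the investigators' own natural-history study, which the documents do not confirm for all 32. Some controls may be lost, and the apparent effect may become less favourable. With five treated infants, early risk sets will be very small, so the treated Kaplan-Meier curve will be unstable at young ages.
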